#### 3 Introduction

This document details the criteria to be used for the definition of the analysis populations and the statistical methodology for analysis for the TOPPIC trial, a randomised trial of 6-mercaptopurine versus placebo to prevent recurrence of Crohn's disease following surgical resection. This document has been compiled according to the Edinburgh Clinical Trials Unit (ECTU) standard operating procedure (SOP) "Statistical Analysis Plans" and has been written based on information contained in the study protocol version 13, dated 29 April 2015.

TOPPIC is a multicentre, randomised, parallel-group, placebo-controlled trial. Treatment allocation is a 1:1 ratio. Patients are randomised to either 6-mercaptopurine or matched placebo control. The aim was to recruit 234 patients.

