#### 4 Statistical Methods Section from the Protocol

The primary outcome variable is postoperative recurrence of Crohn's Disease and it's timing if it recurs. Analysis will be by intention-to-treat and will be based on the application of Cox proportional hazards model. The primary analysis will include terms for the treatment, the variables on which the randomisation was stratified and adjusted for baseline values of previous treatment with 6MP and previous treatment with Azathioprine.

The quality of life variables will be analysed using a repeated measures analysis of covariance to evaluate treatment and treatment by time interactions.

The use of faecal calprotectin as a non-invasive marker of disease recurrence will be examined in two ways. It will be firstly considered as a time dependent covariate in the Cox proportional hazards model described above. Secondly, levels will be compared descriptively between those with negative or positive colonoscopies at 12 and 36 months. Similarly, 6MP drug metabolite levels will be also considered as a time dependent covariate in the Cox proportional hazards model.

Exploratory analyses will investigate the inclusion of the clinical, genetic and serological markers in the model. The models will be used to develop a simple scoring system to predict the risk of recurrence. The sample size will be too small to use a split sample approach to validate the prediction, but the use of a simple scoring system will mitigate to some degree the more extreme effects of using observed regression coefficients to define the risk. During the period after trial recruitment, data from new patients will provide limited short-term validation of the predictions.

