#### Example 1. Data presentation for categorical data

#### Example 2.Data presentation for continuous data

Parameter	Timepoint / visit	Statistic/ category	6-MP	Placebo	Overall
			N=xx	N=xx	N=xx
Parameter	Timepoint x	Mean	XX	XX	xx
		Median	xx	xx	xx
		SD	xx	xx	xx
		Q1, Q3	xx, xx	xx, xx	xx, xx
		Min, Max	xx, xx	XX, XX	xx, xx
		n	xx	xx	xx

All applicable statistical tests will be 2-sided and will be performed using a 5% significance level. 95% (2-sided) confidence intervals (CIs) will be presented. All analyses are seeking to show a difference, rather than equivalence or non-inferiority.

Where there is missing data for an outcome variable, in the first instance, those records will be removed from any formal statistical analysis relating to that outcome variable, unless otherwise specified. In tabulations, numbers of missing observations will be provided, but percentages will not include them.

The main statistical analyses for primary and secondary outcomes will be adjusted for centre and smoking status (from randomisation stratification) and baseline values of 'Previous treatment with 6MP' and 'Previous treatment with Azathioprine' following note from DMC in January 2013. Results of unadjusted statistical analyses will also be presented.

Distributional assumptions underlying the statistical analyses will be assessed by visual inspection of residual plots. Normality will be examined by normal probability plots. If the distributional assumptions for the parametric approach are not satisfied, further data transformation (to alleviate substantial skewness (i.e. normalizing) or to stabilise the variance), or other suitable methods will be considered. This will be documented in the statistical results report together with the reasoning supporting the action taken, if applicable.

All analyses and data manipulations will be carried out using SAS [1].

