#### Pre-assessment

Gender Previous treatment with: 6MP/Azathioprine/Other corticosteroids Infliximab or Methotrexate No immunosuppressants Crohn's disease location & type Previous surgery TPMT Age at randomisation Age at diagnosis Duration of Crohn's disease

Randomisation/Visit 2

Weight, Height Faecal calprotectin Neutrophil count CDAI score IBDQ/EQ-5D/SF-36

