- ii. Time to disease recurrence will be analysed using a Cox proportional hazards model (as detailed in Section 6.5), incorporating calprotectin results as a time dependent covariate, provided there are sufficient outcome events.

Hazard ratios with corresponding 95% confidence interval will be estimated, indicating whether calprotectin levels are surrogate markers of disease recurrence.

5. Thioguanine (TGN) levels of the 6MP drug metabolite samples will be summarised by time and treatment group, both as a continuous measure and categorically following independent blind review. The continuous change from baseline to each time point will also be summarised.

TGN levels of the 6MP drug metabolite samples will also be considered as a time dependant covariate in the Cox proportional hazards analysis of time to disease recurrence (as detailed in 3.ii above). Patients receiving placebo will not be included in this analysis.

- Quality of life will be assessed by the validated indices IBDQ, EQ-5D and SF-36, as follows:
  - a. The values at baseline and each time point, in each of the various subscales of these measures will be summarised (without statistical testing). The change from baseline to each time point will be summarised for IBDQ (average and total) and SF-36 only (physical component score and mental component score).
  - b. Change from baseline in overall IBDQ (average and total) and SF-36 (physical component score and mental component score) indices will be

<sup>3 A negative colonoscopy is defined as a Rutgeert's score of  $\leq$  i1, while a positive colonoscopy is defined as a Rutgeert's score of  $\geq$  i2.

<sup>4 The primary outcome i.e. a Crohn's Disease Activity Index value of greater than 150 together with a 100 point rise in the CDAI score from baseline, together with the need for anti-inflammatory rescue therapy or primary surgical intervention.

modelled using a repeated measures analysis of covariance, fitting terms for treatment, time (visit) and the interaction between treatment and time (visit). Patient and time will be included in the model as random effects.

The estimated treatment effect and 95% confidence intervals will be presented at each timepoint and overall.

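### The quality-of-life analysis of covariance names no baseline score of the scale as a covariate, and it leaves the meaning of random time open

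*SAP*

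**What the plan says.** SAP Section 6.6, item 6b, takes as its outcome the change from baseline in IBDQ (average and total) and in the two SF-36 component scores. The model for it is described as "modelled using a repeated measures analysis of covariance, fitting terms for treatment, time (visit) and the interaction between treatment and time (visit". A separate sentence on random terms reads "Patient and time will be included in the model as random effects". The output is then fixed: "The estimated treatment effect and 95% confidence intervals will be presented at each timepoint and overall".

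Section 5 applies to these scales too, because quality of life sits under the secondary outcomes: "The main statistical analyses for primary and secondary outcomes will be adjusted for centre and smoking status (from randomisation stratification) and baseline values of". The sentence goes on to name two drug histories, one for 6MP and one for azathioprine. Section 5 also calls for unadjusted results.

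Section 4, taken from the protocol, gives the method in general terms: "The quality of life variables will be analysed using a repeated measures analysis of covariance to evaluate treatment and treatment by time interactions". It names no covariate.

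The baseline scores will exist: Section 6.2 lists "IBDQ/EQ-5D/SF-36" among the data from the randomisation visit.

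**The concern.** An analysis of covariance of a change score normally has the baseline value of the same measure as its covariate. Here neither item 6b nor Section 5 names it. A programmer who fits the listed terms plus the Section 5 adjusters obtains a change-score analysis. Any chance difference between the arms in baseline IBDQ or SF-36 then passes into the estimated effect through regression to the mean, and the confidence intervals are wider than they need be. IBDQ is the scale the SAP ranks first for clinical importance, and its optional multiple-imputation analysis reuses this model.

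The second question is what random time means. It could be a visit effect shared by all patients, a slope for each patient, or a loose way of naming the repeated factor. These are different models, and no within-patient covariance is stated. The by-visit effects and the treatment-by-time interaction, which Section 4 says the model is to evaluate, depend on that choice for their standard errors.

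**Working it through.** **Inputs.** From the SAP: "The aim was to recruit 234 patients", allocated 1:1, so 117 per arm. Assumed, because the SAP gives none of them: the correlation r between baseline and follow-up, the SDs, the number of visits, and complete data unless stated. The SAP has no figure of its own on this point to reproduce.

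**1. Loss per visit, equal SDs.** In units of SD², Var(change) = 2(1 − r) and Var(baseline-adjusted) = 1 − r². The SE ratio is √[2/(1 + r)].

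| r | SE, change score | SE, baseline-adjusted | Ratio |
|---|---|---|---|
| 0.3 | 0.1547 | 0.1247 | 1.240 |
| 0.5 | 0.1307 | 0.1132 | 1.155 |
| 0.7 | 0.1013 | 0.0934 | 1.085 |
| 0.9 | 0.0585 | 0.0570 | 1.026 |

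For an assumed effect of 0.35 SD, power goes from 62% to 80% at r = 0.3, from 76% to 87% at 0.5, and from 93% to 96% at 0.7.

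**2. Unequal SDs.** With SD s0 at baseline and s1 at follow-up, Var(change) = s1² + s0² − 2r·s0·s1 and Var(adjusted) = s1²(1 − r²). The difference is (s0 − r·s1)², so adjustment never has the larger variance, apart from a negligible loss of degrees of freedom. Take s0 = 1 and s1 = 1.5:
- r = 0.3: adjusted/change = 2.0475/2.35 = 0.87, so the SE loss is about 7%.
- r = 0.5: 1.6875/1.75 = 0.96, about 2%.
- r = 0.7: 1.1475/1.15 = 1.00, almost nothing.
- r = 0.9: 0.4275/0.55 = 0.78, about 13%. Here r·s1/s0 = 1.35 is above 1, and the loss grows again.

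**3. Chance imbalance.** The SE of the baseline difference is √(2/117) = 0.1307 SD. With equal SDs, the change-score estimate differs from the adjusted one by (1 − r) times the baseline difference. At r = 0.5, an imbalance of one SE moves it by 0.5 × 0.1307 = 0.065 SD.

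**4. Effect averaged over K visits.** Assume that all pairs of occasions correlate at r, and let m = [1 + (K − 1)r]/K. Then Var(change) = m + 1 − 2r and Var(adjusted) = m − r². For r = 0.5 and K = 4, m = 0.625 and the ratio is √(0.625/0.375) = 1.29. For K = 12 it is 1.36. At r = 0.7 the range is 1.15 to 1.18.

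**5. Visit as both fixed and random.** A model with fixed visit, treatment by visit, a random patient intercept and a shared random visit effect was evaluated for six visits and 117 per arm. The SE of the treatment difference was 0.1307 at every visit and 0.0999 overall, for a visit variance of 0, 0.5 or 2. With 30% of records missing, the SEs again did not depend on the visit variance. In a separate simulated data set, the REML log-likelihood was −120.993238 at visit variances of 0, 0.1, 1 and 10, so the data cannot estimate that variance. Only the SE of a single arm's visit mean changed, from 0.0925 to 0.7131 at variance 0.5.

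**6. If only a patient intercept remains.** This implies equal variance and equal correlation across visits. Suppose instead that the raw scores have constant SD and correlation 0.8 per visit step, over six visits. The change at visit k then has variance 2(1 − 0.8^k): 0.40 at the first visit, 1.476 at the sixth, 1.016 on average.
- First visit: pooled SE 0.1318 against true 0.0827, ratio 1.59.
- Sixth visit: 0.1318 against 0.1588, ratio 0.83.
- Sixth minus first: the true variance is 2(1 − 0.8⁵) = 1.345. The exchangeable fit uses the average over all pairs, 0.768, so the ratio is √(0.768/1.345) = 0.76.

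This shows the direction under one assumed pattern. It does not estimate the effect in this trial.

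**The case against.** The list in item 6b is not exhaustive: it also omits the Section 5 adjusters, which do apply. The method is called an analysis of covariance, and many statisticians would include the baseline score without being told. So this may be incomplete specification and not a decision to leave it out. That stands as a view of intent. It does not settle the text, because Section 5 spells out its adjusters and the baseline score is not one of them.

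The size rests on assumed correlations and SDs, and can be close to nil. That also stands. Section 5 allows transformation or other methods after residual plots, but this concerns distributional assumptions and does not supply a covariate.

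A reader might infer two stronger things:
- **That the model has no baseline covariates at all.** It has them through Section 5. What is missing is the baseline score of the scale.
- **That listing visit as both fixed and random makes the by-visit standard errors wrong.** It does not. A shared visit effect cannot be identified beside fixed visit, and it cancels from every between-arm contrast. If random time means a patient-level slope, fixed plus random time is a standard and valid model.

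The compound-symmetry harm therefore belongs to one reading of the text only.

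**Conclusion.** The point holds as an omission that costs efficiency in a secondary outcome, with no bias in the treatment estimate under randomisation. With equal SDs, the by-visit standard error is about 3% to 24% larger than it need be for r from 0.9 to 0.3. A rising SD reduces the loss as long as the slope of follow-up on baseline stays below 1. The averaged effect can lose more, under the exchangeable correlation assumed above.

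The treatment of time is a lesser point of specification. The text does not determine the within-patient covariance. By-visit and interaction standard errors could be misstated if only a patient intercept is fitted and variances or correlations change over three years. The SAP gives no correlations or SDs from which to say by how much.

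**What to change.** In Section 6.6, item 6b:
- Add the baseline value of the scale being analysed, and its interaction with visit, as covariates alongside the Section 5 adjusters. Say whether the baseline score also enters the unadjusted analysis.
- Keep visit as a fixed categorical factor.
- Replace the sentence on random effects. Either state a within-patient covariance, for example unstructured with a named fallback if it does not converge, or say that random time is a patient-level slope.

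The cost is wording and a little programming, and no new data are needed. The fallback matters because an unstructured matrix grows quickly: at an assumed 10 visits it has 10 × 11/2 = 55 parameters. The multiple-imputation analysis of IBDQ should use the same revised model.

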#### 6.7 Safety analyses

- 1. Adverse Events (AEs) will be summarised by treatment and by severity, causality and seriousness. No formal statistical analysis will be performed. A listing will be produced detailing each event, and what happened to the patient subsequently.
- 2. Details will be provided of any patients who become pregnant or who have a partner who becomes pregnant during the study. A listing will be produced detailing each event, and what happened to the pregnancies subsequently.
- Blood safety monitoring tests of interest will be summarised by treatment and visit. Abnormal laboratory results outside of the normal reference range will also be summarised. Results of particular interest are: ALT, Alk Phos, Albumin, CRP, WBC, haemoglobin, neutrophils and lymphocytes.

#### 6.8 Subgroup analyses

The following subgroup analyses are planned:

- i. Patients who are thiopurine naïve (have had previous treatment with either 6MP or Azathioprine)
- ii. Patients who have had previous treatment with Infliximab or Methotrexate
- iii. Patients who have had previous surgery
- iv. Smoking status
- v. Duration of disease ( $\leq 1$  year, > 1 year)
- vi. Age at diagnosis (≤40 years, > 40 years)

The primary and secondary outcomes defining clinical recurrence of Crohn's disease will be analysed for these subgroups. The interaction between subgroup and treatment will be included in the Cox regression model (as described in Section 6.5) to determine if the treatment effect differs by subgroup.

Endoscopic recurrence as defined by Rutgeert's score and the CDEIS score will be summarised and analysed separately for these subgroups in line with the methods described in Section 6.6. Similarly to the subgroup analyses of the primary and secondary outcomes, the interaction between subgroup and treatment will be assessed to determine if the treatment effect differs by subgroup.

#### 6.9 Exploratory analyses

100

Exploratory analyses will be undertaken to investigate the inclusion of clinical, genetic and serological markers as a means of predicting the risk of disease recurrence.

A simple scoring system will be devised by implementing a predictive model which will utilise the markers available.

The number of terms to go into the model will be determined based upon the number of outcome events (i.e. disease recurrence) observed. It is recommended that approximately ten outcome events are observed per explanatory variable for it to merit inclusion in a predictive model.

Appropriate explanatory variables will be selected based on clinical relevance, precision of measurement, and amount of missing data. Correlation between possible explanatory variables will also be considered in order to avoid the same underlying effect being measured by two or more variables.

The model will be evaluated in terms of calibration (i.e. how closely predicted outcomes match actual outcomes) and discrimination (i.e. how well the model distinguishes between low and high risk patients).

This exploratory analysis will not form part of the primary statistical report, but will follow in a separate subsequent report.

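### Section 6.9 of the SAP names no evaluation data and no optimism correction for the exploratory recurrence score; whole-sample bootstrap validation should be added

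*SAP*

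**What the plan says.** SAP Section 6.9 (Exploratory analyses) plans a predictive model built from clinical, genetic and serological markers and turned into a simple score. On performance it says "The model will be evaluated in terms of calibration (i.e. how closely predicted outcomes match actual outcomes" and adds discrimination. It does not say which patients supply the evaluation data. It mentions no bootstrap, cross-validation, shrinkage or other correction.

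The same section contains two safeguards. Model size follows a recommendation of "approximately ten outcome events are observed per explanatory variable". Terms are not picked by outcome tests: "Appropriate explanatory variables will be selected based on clinical relevance, precision of measurement, and amount of missing data", with correlation between candidates also considered. The work goes into a separate, later report.

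SAP Section 4 (Statistical Methods Section from the Protocol) addresses overfitting directly. It says "The sample size will be too small to use a split sample approach to validate the prediction", and then that "the use of a simple scoring system will mitigate to some degree the more extreme effects of using observed regression coefficients to define the risk". It also expects patients seen after recruitment to provide a modest, short-horizon check of the predictions. Section 6.9 does not refer to that check.

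The planned size is in Section 3: "The aim was to recruit 234 patients".

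**The concern.** A risk score is meant for patients other than those it was built on. With the split sample ruled out and no resampling named, the calibration and discrimination of Section 6.9 would by default be apparent performance, computed on the development patients.

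Apparent discrimination is biased upward because the coefficients have been tuned to those patients. The apparent calibration slope carries no information about overfitting. Markers with no predictive value at all could show a C-statistic visibly above 0.5 and a perfect slope, and the evaluation as described would not expose this.

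Section 4 gives sample size as the reason for not validating by split sample. That reason does not apply to bootstrap validation, which uses every patient for both development and validation.

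**Working it through.** The SAP gives no C-statistic, slope or event count for the score, so there is no figure of its own to reproduce. The check is one algebraic step and two simulations.

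**Inputs from the SAP.** N = 234 (Section 3); about ten events per term, terms not chosen on outcome (Section 6.9); three years of follow-up (Section 6.5).

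**Assumptions.** Number of events and strength of the markers, because the SAP states neither.

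**Step 1: in-sample calibration slope.** Let b be the fitted Cox coefficients and LP = Xb. The calibration slope is the coefficient s in the model h(t) = h0(t)·exp(s·LP). In the development data, the derivative of the log partial likelihood in s at s = 1 is b′U(b), where U is the score vector. The fit sets U(b) = 0, so s = 1 is the maximum whatever the true signal. This was 1.000 in every simulated setting.

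**Step 2: optimism, simulation A.** Events of 30, 40, 50 and 70 give 30/10 = 3, 4, 5 and 7 terms. Predictors are independent standard normal, with each coefficient equal to SD/√(number of terms), where SD (0, 0.4 or 0.7) is the true spread of the log-hazard predictor. Follow-up is capped at 3 years, with some earlier censoring. There are 200 data sets per setting, each tested on 2,000 new patients. Optimism = apparent C − C in new patients (differences taken before rounding).

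| True SD | Events / terms | Apparent C | C, new patients | Optimism | Median slope, new patients |
|---|---|---|---|---|---|
| 0 | 30 / 3 | 0.584 | 0.499 | 0.085 | 0.00 |
| 0 | 40 / 4 | 0.581 | 0.501 | 0.080 | 0.03 |
| 0 | 50 / 5 | 0.585 | 0.502 | 0.083 | 0.03 |
| 0 | 70 / 7 | 0.589 | 0.499 | 0.090 | −0.01 |
| 0.4 | 30 / 3 | 0.634 | 0.582 | 0.052 | 0.64 |
| 0.4 | 40 / 4 | 0.640 | 0.586 | 0.054 | 0.59 |
| 0.4 | 50 / 5 | 0.638 | 0.587 | 0.051 | 0.60 |
| 0.4 | 70 / 7 | 0.634 | 0.587 | 0.047 | 0.62 |
| 0.7 | 30 / 3 | 0.698 | 0.672 | 0.027 | 0.86 |
| 0.7 | 40 / 4 | 0.698 | 0.674 | 0.024 | 0.85 |
| 0.7 | 50 / 5 | 0.700 | 0.671 | 0.029 | 0.83 |
| 0.7 | 70 / 7 | 0.698 | 0.668 | 0.030 | 0.81 |

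**Step 3: simulation B, different assumptions.** N = 234; 3-year baseline risk 20% or 35%; 7% drop-out per year; 42 to 86 events; 4 to 8 terms; log hazard ratio per SD of each marker 0, 0.2 or 0.35; 300 data sets per setting, each tested on 1,500 new patients. Optimism in C was 0.08 (no signal), 0.037 to 0.040 (weak) and 0.024 to 0.026 (fairly strong). Slopes in new patients were about 0, 0.69 to 0.74 and 0.85 to 0.86. The two simulations differ somewhat at intermediate signal, so the size is best read as a range.

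**Step 4: does the simple score remove it?** In simulation A the coefficients were also rounded to points. At SD 0.4, apparent C was 0.631 to 0.637 against 0.582 to 0.586 in new patients, a gap of 0.046 to 0.052 compared with 0.047 to 0.054 unrounded. The median slope in new patients was 0.59 to 0.64. Rounding barely helps.

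**Step 5: does the bootstrap remove it?** Corrected C = apparent C − mean over resamples of (C of the resample model in its resample − C of that model in the original data). This was run with 40 resamples in the first 60 data sets of each setting.

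| True SD | Apparent C | Corrected C | C, new patients |
|---|---|---|---|
| 0 | 0.581–0.591 | 0.521–0.530 | 0.498–0.503 |
| 0.4 | 0.630–0.643 | 0.584–0.602 | 0.585–0.587 |
| 0.7 | 0.695–0.703 | 0.666–0.675 | 0.667–0.677 |

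Most of the optimism goes, and nearly all of it when the signal is stronger. Some remains when there is no signal.

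**The case against.** The strongest reply is that Section 6.9 states nothing false. It is silent on the evaluation data and does not exclude resampling, and the detail could be settled in the later report. Section 4 recognises overfitting openly, claims only partial mitigation, and plans some validation in new patients. The limit on terms and the clinical choice of predictors are real safeguards. The largest figures above come from markers with no value at all.

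Much of this stands, and it rules out four stronger readings that a reader might infer:

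- *That the SAP prescribes evaluation on the development patients.* It does not say so. This is the natural reading once the split sample is excluded and nothing else is named, but it remains an inference.
- *That in-sample calibration is worthless.* Only the slope (and average calibration) is uninformative about overfitting. Section 6.9 defines calibration more broadly, and in-sample plots can still reveal non-linearity or misfit caused by rounding to points.
- *That Section 6.9 withdraws the new-patient validation.* Silence does not revoke Section 4. The two sections simply do not refer to each other.
- *That a usable score is an aim of the trial.* The SAP presents it only as an exploratory product, outside the primary statistical report.

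The safeguards do not answer the narrower point. Both simulations already assume about ten events per term and no outcome-driven selection, so the optimism shown is what remains after those rules are followed. Rounding to points leaves it almost unchanged.

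**Conclusion.** The concern holds as a gap in specification. Section 6.9 should say how performance will be validated, because the default reading gives optimistic figures and a method that uses all patients is available.

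The C-statistic would be overstated by about 0.02 to 0.05 with real signal and by 0.08 to 0.09 with none. Calibration slopes in new patients would be about 0.59 to 0.86 with real signal and near 0 with none, against an apparent slope of 1. These sizes rest on assumed event counts of 30 to 86 and assumed marker strengths. The direction was the same in every setting.

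Severity is minor. The analysis is exploratory and separately reported, and it has no bearing on the primary result.

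**What to change.** Add to Section 6.9:

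- Name the patients on whom calibration and discrimination are computed.
- State that performance will be internally validated by bootstrap on all patients, with the number of resamples given. Each resample should repeat every data-driven step: estimating coefficients, any outcome-driven selection, and rounding to points. A choice of terms made on clinical judgement or data quality cannot be re-run by a program and should be held fixed.
- Report the optimism-corrected C-statistic and calibration slope beside the apparent values.
- Consider shrinking the coefficients by the corrected slope before assigning points.
- Cross-refer to the new-patient validation in Section 4 and say whether and how it will be done.

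The cost is a few lines of text, some programming for a report that is already separate, and slightly less favourable reported performance.
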